EXAMINER: A battery of 10 executive function tasks have developed by a NINDS funded project to use in clinical research studies. The tasks take approximately 60 minutes to administer via a computer and result in 12 primary variables. Tasks include: Dot counting (count blue dots on a series of screens and recall the number of dots across screens), N-back (identify whether a series of locations match the location presented 1 or 2 before), Flanker (indicate the direction of an arrow that is flanked by arrows pointing in the opposite direction), Continuous Performance Test (respond to certain stimuli and withhold response to other stimuli on a computer screen), Anti-saccades (move eyes toward a stimulus and moves eyes away from a stimulus), Set-shifting (switch between a homogeneous matching task and a heterogeneous matching task), Phonemic Fluency (name as many words as possible with the same letter), Category Fluency (name as many items as possible in a category), Unstructured Task (complete puzzles within 6 minutes with the goal of earning as many points as possible), and the Social Norms Questionnaire (answer yes no questions about socially appropriate behaviors). Test re-test reliability is .94 and correlated with the FrsBe -0.57 in a multi-neurologic population.

Behavior Rating Inventory of Executive Functions–Adult (BRIEF-A) is a self and informant report questionnaire consisting of 75 statements about executive behaviors. There are three possible responses to items: often, sometimes, never. There are nine subscales: inhibit, self-monitor, plan/organize, shift initiation, task monitor, emotional control, working memory, and organization of materials. Normative self-report (n=1,050) reliability ranges from .73 to .90 for the scales and .93 to .96 for Index and Global Executive Composite scores. While the reliability in a mixed clinical sample (n=233) ranged from .80 to .94 for scales and .96 to .98 for Index and Global Executive Composite scores. Test-retest reliability over 4 weeks averaged .82 to .93 on the scales and .94 for Index and Global Executive Composite scores. The total BRIEF-A score correlates at .84 with the Dysexecutive Questionnaire (Roth, 2005). In a sample of patients diagnosed with TBI, the MI reported a cronbach alpha of 0.96 (Waid-Ebbs et al., 2012). The Metacognitive Index score of the BRIEF-A will be used to detect generalization of treatment effect and impact of specific executive function deficits on treatment gain.

Goal Attainment Scale (GAS) is an individualized outcome measure involving goal selection and a five-point goal scaling that is standardized in order to calculate the extent to which a patient's goals are met. The patient and therapist write goals specific to the patient's needs, such as: +2 able to find 4-5 items; +1 able to find 3 items; 0 able to find 2 items; -1 able to find 1/5 items; -2 unable to stay in store and locate items.

Veteran's Task Manager Smartphone Application (VTM) is a free Smartphone application (AP) specifically developed to utilize the strategies taught in GMT will be loaded from the Apple store or Google store by the participant to their Smartphone (iPhone or Android). Participants will use the application features to break down tasks, estimate time to complete, check off each step as completed, respond to visual/vibrating alert of "Goal" and respond to alert if "On Target". Information, such as accuracy of planned steps, time to complete task, and number of distractions from goal will be collected by the AP. Data will only be transferred via secure messaging in MyHealthVet or shown to the therapist during an individual session

Technology Satisfaction Questionnaire (TSQ) is a questionnaire used to capture satisfaction level for each technological measure used (e.g., GMT, BrainHQ, APT-III, and VTM-APP).

Consensus Sleep Log (CSL) is a measure that patient uses to log sleep/wake times over a one-week period.

Demographics will be collected using the Federal Interagency Traumatic Brain Injury Research forms, including amount and type of productivity (work and unpaid volunteer). Details of TBI events and history will be documented using the Ohio State TBI identification Method which is a standardized procedure for eliciting a person's lifetime history of TBI via a 3-5-minute structured interview.

Statistical Analysis Plan

Aim 1: Determine the treatment effect of attention training combined with GMT in Veterans with mTBI. Hypothesis 1a: GMT plus attention training will significantly improve performance on tests of cognition compared to the control group. 1b: Treatment gains will translate to functional activities compared to controls.

For both Hypothesis 1 and 2: A multiple linear regression model will be used to determine if there is a significant difference between the treatment and control groups in tests of cognition and function. Separate models will be fit for each outcome measure (cTOL, ANT, TOGSS, CRIS) the baseline measure and treatment group indicator will be used as covariates in the model. The Wald test will be used to determine if the coefficient for treatment group is significantly different from zero, indicating a significant treatment effect. Effect sizes for between-group differences will be estimated using the coefficient of the group indicator in the model.

Tertiary analysis: Other moderator variables (Table 2) will be examined to determine whether a linear relationship exists between changes in problem solving, attention or participation. These variables include PCL-5 total score and index scores (such as intrusions), BPI total score, AUDIT-C total score, BDI-II total score, number of concussions, STAXI-2, PSQI, MFIS and CES total score.

Sample Size: A sample size of 50 participants equally randomized into treatment or control groups will yield 80% power to detect an effect size of 0.81³⁹. In other words, if the true improvement in the treatment group is 0.81 standard deviations greater than the control group, then the pilot study has an 80% chance of detecting a significant difference. Based on our preliminary analysis of 14 GMT and 3 BHW controls, we estimate a large effect size of 1.76 (3.16, 0.37) for the cTOL time to first move, a moderate effect size of 0.827 (-0.46, 2.10) for cTOL optimal moves, and a moderate effect size of 0.67 (-0.60, 1.95) for cTOL time to completion⁴⁰.

7. Possible Discomforts and Risks:

The primary hazard to participation in the experimental/clinical neuropsychological measures and interventions is fatigue/frustration. Examiners are trained to respond to such reactions and provide encouragement, breaks, and assistance as needed. Testing or training will be terminated, and the Veteran will be debriefed, in the event of adverse emotional reactions or extreme fatigue, which are very rare. In the event that the participant answers 3 on question 9 of the Beck Depression Inventory (depression questionnaire used during screening) or actively expresses thoughts of harming themselves, the Veterans Crisis Line (also called the National Suicide Prevention Lifeline [contact] press 1 for Veterans Crisis Line) will be called by the research team. This will be performed prior to the subject leaving the sight of the study staff.

8. Possible Benefits:

The proposed project has the potential to provide information that will enable clinicians to target Veterans with disrupted attention neural networks with effective treatments specifically prescribed to a particular component of attention. This will benefit Veterans by improving specific attention components that in turn improve other cognitive processes. The potential benefits far outweigh the minimal risks. Veterans will be reimbursed for each session of their participation.

9. Conflict of Interest:

[name] and [name] have no conflict of interest to declare for this study.

10. Records Management:

The records will be retained and kept in accordance with the VA regulations.

References:

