Recruitment: Patients from the BRRRC recruitment data base will be contacted; clinicians will hand out fliers in North Florida/South Georgia Veterans Health Administration outpatient clinics; letters to inform Veterans with mTBI diagnoses of the study will be mailed; and fliers will be distributed to local Veterans groups and Veteran support centers at community colleges and universities. The proposed study has an existing approved protocol and patients are recruited through a variety of proven methods: patients from the BRRRC recruitment data base will be contacted; clinicians will hand out fliers in North Florida/South Georgia Veterans Health Administration outpatient clinics; letters to inform Veterans with mTBI diagnoses of the study will be mailed; and fliers will be distributed to local Veterans groups and Veteran support centers at community colleges and universities.

Interested participants will be scheduled for an appointment to determine eligibility criteria. Once potential participants are deemed eligible, written informed consent will be obtained from each subject by the PI or trained research assistant. The PI or trained research assistant will explain the purpose of the project and describe the procedures to be followed. Participants will be asked to sign an informed consent after the purpose of the project, risks, and benefits have been fully explained in language a layperson can understand.

Participants can choose to participate in GMT or individual cognitive treatment as part of clinical care if they do not wish to participate in research.

Once the participant signs consent, any treatment with the investigators will be discontinued until the follow-up testing has been completed.

Once Veteran meets inclusion criteria, they will identify an informant that observes their functional behavior at least 2-3 times a week. The informant will be scheduled for an appointment for consent and to complete the BRIEF-A questionnaire. They will receive a phone call once a week to answer whether the homework was easy or difficult for the Veteran and see if there are specific cognitive issues that need to be addressed.

Due to the COVID 19 outbreak, this protocol has been modified to reduce the participants' risk of contracting COVID-19 from in-person exposure during treatment. GMT and attention training will be conducted by Telehealth using the VA Video Connect (VVC) service.

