Randomization Procedure: 25 of the Veterans will be randomized to treatment while 25 will engage in BHW/movies as control participants. The Pocock-Simon covariate adaptive randomization procedure will be used so that, for each PTSD severity category, approximately 50% (25/25) of Veterans are assigned to treatment group; consequently, there will be approximately equal proportion of PTSD participants assigned to the treatment and control groups.

Each group of the 25 treatment and 25 control participants will also be randomized to training to complete the Test of Grocery Shopping skills in a virtual setting (V-Mart) during session 7 or 8.

Intervention

GMT: is a 10-session intervention to improve planning and problem solving. Interactive Power Point modules are administered by a cognitive therapist. Each session builds on the steps of a five-stage planning and problem-solving strategy. Veterans will be taught to generate and verbalize the following five-steps: "stop-what am I doing?", "define the goal", "list the steps", "learn the steps"; then, "check-am I doing what I planned?" The five-stage strategy is then incorporated into a variety of activities in the laboratory and in-home assignments. At each session, the participant discusses utilization of the strategies in daily life and reviews progress. The following steps are taught during simulated tasks: 1) Identify Main Goal; 2) Break down task into sub-goals and steps for each goal; 3) List supplies needed; 4) Recognize potential barriers to completing goal; 5) Determine strategy to accomplish task; 6) Prepare to begin task with "presence of mind" exercise; 7) State goal out loud; 8) Begin task and stop self frequently to state main goal out loud and check to be sure one is working toward the goal (on target).

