Attention Training: Veterans will also engage in **BrainHQ™** attention training at home for one-hour, five days/ week comprised of selected components of BrainHQ from Posit Science Corporation (Table1). Once a week the Veteran will review and engage in Brain HQ with the therapist during a second two-hour weekly tele-health session. This web-based computerized CRT modality of cognitive training is a restorative or “bottom-up” approach that targets basic cognitive skills such as arousal and vigilance processes, attention and information processing, and directly engages fundamental attention-control skills through repetitive graded exercises. BrainHQ is software designed such that the speed and complexity of exercises increase as the user’s performance improves to consistently maintain a high proportion of successful trials while gradually increasing task demands. BrainHQ has been designed as a web-based platform, and participants can perform tasks at home on their own home computers. Veterans will be given a code and password from the research staff to sign into Brain HQ so that their personal information is not recorded. Speed and accuracy as well as time spent engaged are downloaded directly from the Brain HQ website by the research staff. Only the PI will have the key to code names to identify the link to the Veteran. Therapist and Veteran will identify functional activities in the home that require attention skills and homework will be assigned to practice functional tasks to complete using Veterans Tasks Manager Smartphone AP and the Goal Attainment Scale.

Table 1. Selected BrainHQ™ Tasks	
BrainHQ™ Task	Cognitive Domain Trained
“Divided Attention”	Divided attention
“Target Tracker”	Divided attention
“Double Decision”	Useful field of view & visual processing speed
“Mixed Signals”	Selective attention
“Freeze Frame”	Alertness

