Control Group: Participants that are randomized to this group will provide a control for repeat testing and will provide similar characteristics with the treatment group, such as severity of PTSD. To equate for time and exposure to therapist, the participants will engage in a Brain Health Workshop (BHW) and watch geographic movies. BHW was developed specifically for consistency with GMT session length and contact with the facilitator⁴⁹. BHW is an education presentation on brain function and cognitive principles of learning with homework (readings assigned) and quizzes on information covered. To match time and contact of attention training, control participants will meet with the therapist for a separate two-hour session from BHW and watch geographic movies followed by a short quiz. This will equate the amount of time and contact experienced by the treatment group for both the GMT and attention training sessions.

Measurement: Veterans with mTBI will qualify for the study if they demonstrate a deficit in attention as measured by formal neuropsychological testing and pass effort testing. The following measures (Table 2) will be administered at week 1 (before intervention), week 11 (after intervention) and at week 36 (six months after intervention). The primary outcome measures for Aim 1, will be the computerized Tower of London (cTOL)³⁸ and the Test of Grocery Shopping Skills (TOGGS).

The following measures will be administered by an email link from the University of Florida REDCap application: Combat Exposure Scale, Neurobehavioral Symptom Inventory, Beck Depression Inventory, Alcoholic Use Disorders Identification Test, PTSD Checklist for DSM5, Brief Pain Inventory, Behavioral Rating Inventory of Executive Function for Adults, and State Trait Anger Expression Inventory.

Table 2. Study Measures			
Domain	Purpose	Administration session	Measure(s)/Minutes to Administer
Pre-Treatment Screening/Assessment			
Attention	Attention impairment	Weeks	RBANSAttention index
Effort	Determination of potential suboptimal effort	1	*TOMM/5
Word-reading	For group matching—estimation of pre-morbid cognitive ability	1	*NAART/10
Primary Outcome Measures			
Executive Function	Assesses problem-solving, planning and attention	1, 11, 36	cTOL/20
Functional	Assess performance of a complex task	1, 11, 36 7 or 8	ToGSS./30 V-Mart/20
Secondary Outcome Measures – Cognition			

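### The control arm is described as matched on time, but only therapist-session time is matched: about 4 to 5 hours a week of home BrainHQ has no stated counterpart, which limits what a group difference can be credited to

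*Combined protocol and SAP*

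**What the plan says.** All of this is in Section 6 (Research Plan) of the combined protocol and SAP.

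- **Treatment arm, home.** The Attention Training paragraph prescribes "attention training at home for one-hour, five days/ week comprised of selected components of BrainHQ".
- **Treatment arm, with therapist.** The same paragraph adds: "Once a week the Veteran will review and engage in Brain HQ with the therapist during a second two-hour weekly tele-health session".
- **Treatment arm, other home work.** It also says that "homework will be assigned to practice functional tasks to complete using Veterans Tasks Manager Smartphone AP and the Goal Attainment Scale". No hours are given. GMT itself "is a 10-session intervention to improve planning and problem solving", with home practice supported by the smartphone application.
- **Control arm.** The Control Group paragraph gives equal time and equal therapist exposure as the purpose of the control activities. BHW stands against GMT on session length and facilitator contact. For the other component: "To match time and contact of attention training, control participants will meet with the therapist for a separate two-hour session from BHW", spent on geographic movies and a short quiz. The paragraph closes: "This will equate the amount of time and contact experienced by the treatment group for both the GMT and attention training sessions". BHW carries assigned readings as homework, of unstated length.
- **Analysis.** The Statistical Analysis Plan compares the arms with a regression on the baseline measure and a group indicator, one model per outcome (cTOL, ANT, TOGSS, CRIS).

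**The concern.** Two statements in the Control Group paragraph list time separately from contact, and one of them refers to the time of attention training without restricting it to sessions. As the plan defines attention training, most of its scheduled time is unsupervised home practice. A reader of the protocol, or of a paper that repeats its wording, would take the arms to be matched on time when they are matched only on therapist sessions.

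What is at stake is attribution. An equal-time control removes hours of activity and engagement as an explanation, so that a difference points to what was trained. Without it, extra home computer practice and engagement are a plausible rival explanation. This bears most directly on the Tower of London (cTOL) and the Attention Network Task (ANT), which are timed and done on a computer. It bears less directly on the Test of Grocery Shopping Skills (TOGSS), which is done in a real store.

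The plan has some interest in content. The ANT description looks to how individual attention networks respond to training, and Section 8 (Possible Benefits) hopes for treatments aimed at particular components of attention. The Background also criticises earlier studies for often not reporting time spent in attention training.

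**Working it through.** The plan gives no total of hours for either arm, so there is no stated figure to reproduce. The check adds up the scheduled components.

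**Inputs stated in Section 6**

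- Home BrainHQ, treatment: 1 h × 5 days = 5 h/week.
- Therapist-led attention session, treatment: 2 h/week.
- Therapist-led movie session, control: 2 h.
- Home counterpart to BrainHQ, control: none described.

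**Assumptions**

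- The movie session is weekly, as its treatment counterpart is.
- Training lasts about 10 weeks, inferred from 10 GMT sessions and post-testing at week 11; range 9 to 11.
- One of the five BrainHQ hours might be done inside the therapist session, leaving 4 h/week at home. The text does not settle this.

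**Step 1: therapist-led time.** Attention component: 2 h against 2 h. GMT against BHW: matched by BHW's design. Session time is equal on paper.

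**Step 2: scheduled attention-training time against its control counterpart**

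- With 5 h at home: 5 + 2 = 7 h/week against 2 h/week; 7 / 2 = 3.5.
- With 4 h at home: 4 + 2 = 6 h/week against 2 h/week; 6 / 2 = 3.0.

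**Step 3: unmatched home hours over the training period**

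| Weeks | 4 h/week | 5 h/week |
|---|---|---|
| 9 | 36 h | 45 h |
| 10 | 40 h | 50 h |
| 11 | 44 h | 55 h |

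**Step 4: could control homework close the gap?** The BHW readings belong to the workshop that is set against GMT, and GMT has home practice of its own. To close the gap, the readings would have to exceed the treatment arm's other homework (GMT practice and functional tasks) by 4 to 5 h/week. Nothing in the documents says that they do.

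**Step 5: would the planned data show it?** BrainHQ time is downloaded from the vendor's site, and the smartphone application records time to complete tasks; both belong to the treatment arm's training. The weekly call to the informant asks whether homework was easy or difficult, not how long it took. No record of control homework hours is described.

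**Step 6: could the model adjust for it?** The planned model has no term for training time, and adding one would not help. BrainHQ hours exist in one arm only, so no control participants have comparable hours from which to separate the effect of hours from that of the arm.

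The sample-size statement (50 participants, 80% power, effect size 0.81) does not depend on any of this.

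**The case against.** The strongest defence is that the closing sentence of the Control Group paragraph speaks of sessions, and for sessions it is true. The two broader statements can be read the same way, since one is tied to therapist exposure and the other to meeting the therapist. Home BrainHQ is also a prescribed part of the intervention, so its hours are part of what is being tested and not a confounder from outside. Hypothesis 1 asks whether GMT plus attention training does better than control, which is a whole-package question. Whether a pilot control should match home activity as well as contact is a legitimate design choice.

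Much of this stands, and it rules out several stronger readings that a reader might infer:

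- **That the closing sentence is false.** It is accurate for therapist-led time. The difficulty lies in the broader wording before it.
- **That the primary comparison is confounded or invalid.** It is not. Randomised arms are compared on the package as prescribed, home hours included.
- **That extra hours explain a difference as well as content would.** Nothing in the documents ranks the two. Extra hours are a plausible rival and no more.
- **That controls receive about half the treatment arm's total activity time.** If GMT and BHW sessions also last two hours, the listed components come to 80 to 90 h against 40 h. But that session length is only inferred from the two-hour BrainHQ session being called the second of the week, and homework in both arms is left out. A share of total time cannot be computed.
- **That the arms differ in delivery mode.** The Recruitment text says that "GMT and attention training will be conducted by Telehealth using the VA Video Connect (VVC) service" and does not mention BHW or the movies. That is silence about the control sessions, not evidence of a difference, and it has no bearing on home hours.

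What the defence does not answer is that the paragraph claims to match the time of attention training, while the plan's own definition of attention training includes home hours that have no match.

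**Conclusion.** The concern holds in a limited form. Therapist-session time and contact are matched on paper; total activity time is not shown to be. The treatment arm has 4 to 5 h/week of home BrainHQ with no stated control counterpart, about 40 to 50 h over 10 weeks (36 to 55 h across 9 to 11 weeks). The weekly figure rests on the text, with its lower end allowing for one hour inside the session; the totals rest on the inferred duration.

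The trial can conclude that the package, including its home practice, does or does not outperform contact-matched education. It cannot conclude that the content of the training, apart from extra hours of home computer practice and engagement, produced a difference. The caution applies mainly to cTOL and ANT. The analysis model, the power and the validity of Hypothesis 1 are unaffected.

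**What to change.** 1. **Reconcile the Attention Training and Control Group paragraphs.** Replace the time-matching statements with wording such as: *Therapist-session time and contact are matched between arms; total activity time is not.*
2. **Word the Aim 1 conclusion accordingly:** the whole package, including home practice, versus contact-matched education.
3. **Record control homework time** alongside the BrainHQ time already downloaded, and report home hours by arm.

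The cost is a wording change, one extra logged item for controls and a narrower attribution claim. Giving controls a home activity of matched length is a separate design trade-off for the investigators, and this correction does not depend on it.

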Method: This is a randomized control pilot study to determine effectiveness of GMT plus Attention Training in 50 Veterans with mTBI. The research design is a parallel study with randomization to treatment or control with test administration at pre/post and six months following treatment. A multiple linear regression model will be used to determine if there is a significant association between treatment effect and comorbidities such as PTSD, depression, anxiety, pain, sleep, substance abuse, etc.

4. Background:

Problem. TBI can be the beginning of a disease process that produces change that continue years after injury resulting in debilitating chronic TBI symptomatology^{1,2}. Some studies find that up to 30% of people that have sustained mTBI have persistent symptoms³. Persistent symptoms following mTBI have been related to diffuse axonal injury⁴ or neuroinflammatory reactions⁵. Enduring cognitive deficits after mTBI present barriers to full functional recovery and re-entry into societal roles. Executive dysfunction, poor attention-concentration, and memory difficulties are the most persistent disabilities faced by mTBI survivors^{6,7}. An estimate 44% of Veterans with mTBI also have PTSD⁸ with overlapping symptoms. Attention problems are reported by 50% of combat Veterans⁹ which are requisite for other cognitive processes that are vital to everyday functioning such as memory, problem solving, language skills, and the cognitive control of behavior. Associated comorbidities also impair cognition making it difficult to diagnose and treat Veterans with mTBI. These comorbidities include pain¹⁰, substance abuse¹¹, anxiety¹², depression¹³, fatigue¹⁴ and sleep disturbances¹⁵ that also specifically impact attention. Cognitive deficits are the most debilitating following mild to severe TBI and can lead to long-term disability and immense economic burden¹⁶.

Gaps in Knowledge.

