National Adult Reading Test (NART) is an oral reading test consisting of 50 words (Nelson and Willison, 1991). The NART can be used to estimate premorbid intelligence and will be used as a screen. Similar to Levine et al. (2007), we will use the cut off score of > 90 as an inclusion criterion to ensure that frontal lobe impairment is not the result of low premorbid intelligence, and that the subject will be able to read the material during treatment.

Test of Memory Malingering (TOMM): is frequently used to detect poor effort on neuropsychological assessment and has been validated with TBI patients (Tombaugh, 1996; Slick et al., 2004; DeBoar, 2007). This test will be used to screen out patients scoring 45 or below on Trial 2 or the Retention Trial (Trial 1 scores will not be used) to provide a level of confidence to the results of outcome measures.

Repeatable Battery for the Assessment of Neuropsychological Status (RBANS): is a cognitive screening instrument The RBANS is composed of 12 subtests that yield 5 index scores and a total score. The subtests of List Learning and Story Memory comprise the Immediate Memory Index; Figure Copy and Line Orientation yield the Visuospatial/Constructional Index; Picture Naming and Semantic Fluency yield the Language Index; and Digit Span and Coding comprise the Attention Index. Four subtests make up the Delayed Memory Index, specifically, List Recall, List Recognition, Story Recall, and Figure Recall (Randolph, Tierney, Mohr, & Chase, 1998). Administration is approximately 20 minutes and has been used to assess cognition in mTBI (Cooper et al., 2010). An attention score of 1.5 SD below the mean will be used to include participants with an attention deficit. The index scores of the RBANS will also be used to characterize the patient's cognitive capacity and to determine whether aspects of cognitive ability impact response to treatment.

2. Primary Treatment Outcome Measures:

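### Table 2 says the word-reading score is collected for group matching, but no allocation or analysis step uses it; prespecify it as a covariate in the primary-outcome models and correct the table

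*Combined protocol and SAP*

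**What the plan says.** Five places bear on the word-reading score.

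- **Section 6, Table 2 (Pre-Treatment Screening/Assessment).** The score is taken at week 1, and its purpose is "For group matching—estimation of pre-morbid cognitive ability".
- **Section 6, exclusion criterion 4, and Description of Measures, Screening Measures.** A score below 90 excludes the Veteran. The description of the test says: "The NART can be used to estimate premorbid intelligence and will be used as a screen".
- **Section 6, Randomization Procedure.** Allocation is by Pocock-Simon "so that, for each PTSD severity category, approximately 50% (25/25) of Veterans are assigned to treatment group". The balance claimed from it is that "there will be approximately equal proportion of PTSD participants assigned to the treatment and control groups". The other randomization in that section concerns the virtual-store training and has nothing to do with reading ability.
- **Statistical Analysis Plan, Hypotheses 1 and 2.** In each outcome model, "the baseline measure and treatment group indicator will be used as covariates in the model". No other term is named.
- **Statistical Analysis Plan, Tertiary analysis, and the Abstract.** The moderator list begins "These variables include PCL-5 total score and index scores (such as intrusions), BPI total score, AUDIT-C total score" and goes on to depression, concussions, anger, sleep, fatigue and combat exposure. The Abstract describes a regression for the "association between treatment effect and comorbidities such as PTSD, depression, anxiety, pain, sleep, substance abuse, etc". Neither names the reading score. The RBANS description gives the question of whether cognitive ability affects response to the RBANS indices.

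**The concern.** The plan states a design purpose for a baseline variable and then provides no mechanism for it. An entry cut-off removes low scorers from both arms, but it does not match the arms above the cut-off. A report that follows Table 2 could therefore describe the groups as matched on premorbid ability when nothing ensured it.

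The variable is not incidental. The plan screens on it so that impaired executive performance is not mistaken for low premorbid ability, which treats it as relevant to the primary outcome domain. With 25 per arm, a visible difference on such a variable is not rare. If one appeared, a decision at that stage to adjust for it would be post hoc. Precision also has some value here: two of the three preliminary cTOL effects in the Sample Size paragraph, 0.827 and 0.67, lie close to or below the 0.81 SD that the trial is sized to detect.

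**Working it through.** **Inputs from the documents:** 25 per arm; effect 0.81 SD; power 80%. **Assumed:** two-sided alpha 0.05, because the documents give neither alpha nor sidedness; and R², the share of outcome variance left after baseline that the reading score explains. The documents give no correlation, so R² is shown over a range from 0 to 0.15.

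**1. The plan's own figure.** For a two-sample t-test, the noncentrality is 0.81 × √(25/2) = 2.86 with 48 df, and power is 80.1%. With the planned baseline covariate (47 df), treated as free of estimation cost, it is again 80.1%. The stated 80% reproduces.

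**2. Chance imbalance.** For a covariate not balanced by design, the difference between arms has standard deviation √(2/25) = 0.283 covariate SDs.

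- At least 0.3 SD: P(|Z| > 0.3/0.283) = 0.289, about 29% of trials.
- At least 0.5 SD: P(|Z| > 0.5/0.283) = 0.077, about 7.7%.

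**3. What an imbalance does to one estimate.** An imbalance d in the score moves an estimate that omits it by d × √R². At d = 0.3 this is 0.3 × √0.05 = 0.07 SD to 0.3 × √0.15 = 0.12 SD. This is less than half the standard error of 0.283 and is already contained in it.

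**4. Effect of adjustment on power, simple formula.** Replacing 0.81 by 0.81/√(1 − R²) with 46 df gives 80.1% at R² = 0 and 82.0%, 84.0% and 86.0% at 5%, 10% and 15%. This is too favourable, because it ignores the chance correlation between the added covariate and group.

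**5. Effect of adjustment on power, by simulation.** 40,000 trials per setting, 25 v 25, independent normal covariates, effect 0.81 residual SD, both models fitted to each trial:

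| R² | Baseline only | Baseline + score | Change (points) |
|---|---|---|---|
| 0 | 79.5% | 78.5% | −1.0 |
| 0.02 | 79.6% | 79.4% | −0.2 |
| 0.05 | 79.5% | 80.7% | +1.2 |
| 0.10 | 79.1% | 82.1% | +3.0 |
| 0.15 | 79.2% | 84.4% | +5.2 |

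Monte Carlo error is about √(0.8 × 0.2/40,000) = 0.2 points per entry.

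**6. Cross-check on the break-even.** With N = 50 and k independent normal covariates, the variance of the group coefficient is inflated on average by (N − 3)/(N − 3 − k). This is 47/46 for baseline alone and 47/45 with the score, a ratio of 46/45. The score must therefore explain about 1 − 45/46 = 2.2% of residual variance to pay for itself, which agrees with the simulation.

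**The case against.** The strongest reply is that this is a wording slip and no more. The text states the score's job, which is screening, and the score does that job in both arms. The matching phrase may be left over or merely descriptive. Allocation is random, the test keeps its error rate without the covariate, and each model already adjusts for the outcome's own baseline. Covariate choice in a pilot of 50 is a design judgement.

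Much of this stands, and it rules out several stronger readings that a reader might draw:

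- **That the comparison is biased.** It is not. The score is balanced in expectation, and the shift in step 3 is ordinary chance variation. Step 2 also concerns the raw score; once baseline is in the model, only the part of the score that baseline does not explain matters.
- **That adjustment is free, with power of 82 to 86%.** Step 5 shows a loss of about 1 point at R² = 0 and a smaller gain than the simple formula gives. Low R² is plausible, since the cut-off narrows the score's range and baseline absorbs shared ability.
- **That every outcome model needs the score.** The plan's reason for measuring premorbid ability bears on executive performance. Nothing in the documents ties it to CRIS participation, and the case for ANT is not made either.
- **That it should become a second allocation factor.** This could weaken balance on PTSD severity, the factor the protocol puts first. It is a trade-off, not a correction.
- **That the score is discarded, or that PTSD severity is stated to be the sole factor.** Nothing says the score will go unreported, and the randomization text names PTSD severity without calling it the only factor. It remains true that no step names the score.

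The reply does not remove the mismatch. The table states a purpose that nothing else in the plan serves, and the choice of covariate has to be fixed in advance to be credible.

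**Conclusion.** The point holds in limited form. Table 2 promises matching on premorbid ability, and neither the allocation nor any model delivers it. The consequences are a possible misdescription of the groups, a 29% chance of an imbalance of at least 0.3 SD, and possibly some lost precision. The validity of the primary test is not in question, and the sample size of 50 need not change.

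Adjusting for the score changes power by about −1 point if it adds nothing beyond baseline, about zero at 2% of residual variance, and about +1 to +5 points at 5 to 15%. These figures rest on two-sided alpha 0.05, 25 analysed per arm, independent normal covariates and the assumed R². This is a cheap improvement with a small downside, not the repair of a serious defect.

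**What to change.** In the Statistical Analysis Plan, under Hypotheses 1 and 2, add the pre-treatment word-reading score as one prespecified continuous covariate in the cTOL and TOGSS models, beside the outcome's baseline and the group indicator. Do this before outcome data are seen. In Table 2, replace the matching purpose with eligibility screen and prespecified covariate. Name the instrument consistently at the same time: the table lists the NAART, while the exclusion criteria and the measure description refer to the NART.

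The cost is one sentence in the SAP, one table entry, one degree of freedom per model and about 1 point of power in the worst case. No new data are needed, because the score is already collected at week 1. If the sponsor prefers to leave the models as they are, the matching phrase should still come out of Table 2; that would only tidy the wording and would bring no gain in precision.
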